3.2. Informed Consent

Written informed consent will be obtained from every subject. Once consented, the subject will be considered enrolled in the study. Screen failure data will be collected. A subject is considered a screen failure post signing the informed consent.

The informed consent interview will be performed, and each subject will be given personal time and the opportunity to ask questions. The time for decision making prior to giving consent or declining participation will include the time to slowly read and to discuss the consent form. The IUS (ultrasound only probe) and OA/US (duplex probe) imaging procedure will be performed after consent. The subject will receive a copy of the Informed Consent Form for their records.

Upon enrollment, subjects receive a subject number that will be used on all documentation for the subject throughout the study. Subject numbers will be assigned in ascending order, and numbers will not be omitted or reused. The subject number is coupled with the site identification number for

unique identification of each subject.

3.3. Enrollment Failures

Subjects deemed enrollment failures according to the quality assurance review or failure to complete the biopsy evaluations for BI-RADS 3 (as applicable), BI-RADS 4 and 5 will be replaced during the active enrollment period of the study. The following subjects will be considered enrollment failures and will be followed until all AEs are resolved:

- Subjects found to be ineligible after the scan is conducted
- Subjects for whom the study device scans do not pass review (Imaging Core Lab Quality Assurance Radiologist (QAR) review)
- BI-RADS 3 (as applicable) 4 and 5 subjects who have incomplete or unusable biopsy results

4. STUDY PROCEDURE

4.1. Study Device

The study will use the Gen 2 Imagio to generate grayscale ultrasound only (IUS) and OA/US images as applicable depending on the subjects mass or abnormality. The Gen 2 OA/US duplex probe and device is an investigational device in the US.

The Imagio OA/US probe and device will not be used to make any subject clinical decisions during this study.

4.2. Operator Credentials and Training

The Imagio system will be operated only by a trained and qualified healthcare provider.

The Subject, the Imagio Breast Imaging System User, and everyone else in the scan room must always wear Seno approved laser protective eyewear when the Imagio Breast Imaging System is powered on and the laser is enabled

4.3. Subject Data

Data to be collected:

- Gender
- Age
- Race
- Ethnicity
- Fitzpatrick skin type
- Breast and lymph node medical/surgical history

- Height
- Weight
- Inclusion/Exclusion criteria review
- Breast Mass location and depth and size
- Breast Mass feature Scores
- Image Artifact Score
- Lymph node location and size and depth
- Lymph Node Scoring
- Standard of Care (SOC) Imaging POM and BI-RADS
- Imago IUS POM and BI-RADS using ultrasound only probe and OA/US POM and BI-RADS post SenoGram for breast mass
- IUS ultrasound only probe imaging, duplex OA/US probe imaging (doppler and elastography images as applicable with duplex OA/US probe in ultrasound only mode), and SOC imaging for each breast study mass and study lymph node (as applicable)
- Breast biopsy images for ultrasound only probe and duplex OA/US probe in ultrasound only mode and pre and post biopsy duplex OA/US probe in OA mode images as possible
- Mass and lymph node pathology and surgical report for BI-RADS 3 (as applicable), 4 and 5 masses
- Device Adverse Events/Effects
- Reason for End of Study

4.4. Scan Procedure and Imago Imaging

Each subject depending on BI-RADS score will have the breast and as applicable the axillary lymph nodes imaged with the ultrasound only probe and the Imago OA/US duplex probe. The expected duration of a subject's participation would be a total of one visit. The duration of the imaging session will be determined by the subject's availability and may be up to approximately 60 minutes in duration. If there are technical difficulties, the scan procedure may extend beyond this timeframe. In addition, if there are technical issues with the saved images, the subject may be asked to return to repeat the scan procedure.

Imago imaging will be done per the Scan Protocol for each subject.

1. Elasto and/or Doppler and scan with gray-scale ultrasound only probe as possible
2. Elasto and/or Doppler and Scan with ultrasound portion of the duplex OA/US probe as possible.
3. Biopsy imaging as possible (up to 3 subjects only) with the gray scale only probe and the duplex OA/US probe.
 - a. Gray-scale ultrasound only probe and OA/US duplex probe in ultrasound only mode:

- i. Pre biopsy.
- ii. Needle pre-fire and post fire
- iii. Post biopsy

b. Duplex OA/US probe in OA mode

- i. Pre biopsy
- ii. Post biopsy

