Intervention	Each subject will have the breast and, as applicable, the axillary lymph nodes imaged with the Gen 2 Imagio system.
Duration of study visit	One visit of up to 60 minutes unless Imagio imaging needs to be done again
Total duration	6 months
Clinical investigation population	
Sample size	
A maximum of 38 healthy subjects ≥ 18 years old will be enrolled in the study. The 38 subjects will include the following:
 
 - 4 BI-RADS 1 - 4 BI-RADS 2 - 8 subjects with BI-RADS 3 - 8 subjects with BI-RADS 4a - 4 subjects with BI-RADS 4b - 4 subjects with BI-RADS 4c - 6 subjects with BI-RADS 5
Inclusion criteria	
Subjects must meet the following criteria:
 
 - Signed and dated informed consent, prior to participating - At least 18 years of age - Have been referred for a breast US because of a breast lesion/mass finding via a palpable lump or per standard of care imaging - Willing and able to comply with protocol required scans
Exclusion criteria	
Subjects who meet any of the following criteria will be excluded:
 
 - Pregnant or lactating - Has a condition or breast impediment at a location where the duplex probe will be in contact with the subject, which could interfere with the intended field of view - Photo-toxicity associated with currently taking, or having taken, photosensitizing agents within the previous 72 hours - Currently undergoing phototherapy - History of photosensitive disease or undergoing treatment for a photosensitive disease and is experiencing photosensitivity

	
 - Previous adverse reaction to medical laser procedures - Prior benign excisional breast biopsy on breast of interest within the past 18 months - Current mastitis -Prisoners
Statistical analysis	

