4.6. Minimization of Bias

Potential for bias during this clinical investigation has been minimized by a well-controlled design, expected conduct under the terms of an approved study protocol, use of specific inclusion and exclusion criteria, careful definitions for study procedures and outcomes and prospectively defined methods of data analysis. No blinding/masking will be conducted.

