5. SCHEDULE OF EVENTS

Table 1 shows the schedule of events for this study

Table 1. Schedule of events

Evaluation	Screening/ Enrollment/Baseline Imaging Visit ¹ Day 0	Breast and Lymph Node Biopsy Visit (if not done on same day as baseline) May be repeated if issue with initial biopsy *Up to 45 days from baseline	Breast and Lymph Node (as applicable) Surgery *Up to 60 Days from baseline
Informed Consent	X		
Breast/Lymph Node Medical History	X		
I/E Criteria	X		
CDU (including elastography and doppler as applicable) and SOC Imaging	X		
Imagio Imaging (including Elastography and Doppler as applicable) of breast and lymph node (as applicable). This includes biopsy imaging as applicable	X ²	X	
SOC + Imagio Imaging uploaded to Core Lab	X		
SOC Imaging, Imagio IUS and/or IUS+OA POM and BI-RADS Scoring	X		
Pathology/Surgical Reports as applicable		X	X
Adverse Event/Effect	X		
End of Study	X ³	X ³	X ³

¹The Screening/Enrollment/ Imaging, and Biopsy Visits may take place on the same date as the discretion of the investigator

² BI-RADS 1 and 2 abnormalities will be scanned with the ultrasound only probe and possibly the duplex OA/US probe. BI-RADS 3-5 masses will be scanned with both probes.

³ Study will end at the final definitive diagnosis of the breast mass which could include confirmation via surgery report

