7.1.3. Analysis of Study Endpoints

Breast mass site pathology diagnosis (benign, malignant, high risk) will be summarized by presenting the frequency and percentage of breast masses in each BI-RADS category. A listing of the pathology results (benign specification, malignant specification, high risk specification) will be presented.

Breast mass feature scores

Each of the following breast mass feature score data will be summarized by presenting the mean, standard deviation, number of observations, median, quartiles, minimum, and maximum:

- For IUS:
 - External peripheral zone score (range 0-5)
 - External capsular/boundary zone score (range 0-6)
 - Internal shape score (range 0-5)
 - Internal sound transmission score (range 0-5)
 - Internal echotexture score (range 0-5)
- For OA/US:
 - External peripheral zone radiating vessel score (range 0-5)
 - External capsular/boundary zone vessel score (range 0-6)
 - Internal vessel score (range 0-5)
 - Internal deoxygenated blush score (range 0-5)
 - Internal total hemoglobin score (range 0-5)

3. Imago/OA/US POM and BI-RADS for breast using SenoGram

Investigator POM for breast using SenoGram will be summarized by presenting the mean, standard deviation, number of observations, median, quartiles, minimum, and maximum. Investigator BI-RADS for breast using SenoGram will be summarized by presenting the frequency and percentage of breast masses in each BI-RADS category. SenoGram LOM for breast will also be summarized by presenting the mean, standard deviation, number of observations, median, quartiles, minimum, and maximum.

Lymph node scoring

Lymph node scoring (shape score, cortical thickness score, margin score, hilar compression-displacement score, and size) will be summarized by presenting the frequency and percentage of lymph nodes in each category. The total score will be summarized by presenting the mean, standard deviation, number of observations, median, quartiles, minimum, and maximum. Imago IUS classification of lymph node will be summarized by presenting the frequency and percentage of lymph nodes in each category.

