8.2. Blinding

Subjects will not be blinded to best practice study procedures but will not have access to the Imago OA/US evaluation result.

The site investigators will have access to all subject data including the Imago OA/US images and will assess and document the results of the OA/US study by completing the electronic data entry form (electronic case report form (eCRF)).

The site investigators will have access to the background clinical information and to the subsequent histopathology report.

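### Does the plan need a rule for which score is analysed when an Imagio scan is repeated?

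*Combined protocol and SAP*

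**What the plan says.** A second Imagio session is allowed in two places. The synopsis describes the visit as "One visit of up to 60 minutes unless Imagio imaging needs to be done again", and section 4.4 adds that "if there are technical issues with the saved images, the subject may be asked to return to repeat the scan procedure".

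Table 1 in section 5 has no column for such a session. The rows "Imagio IUS and/or IUS+OA POM and BI-RADS Scoring" and "SOC + Imagio Imaging uploaded to Core Lab" each carry one mark, under Day 0. Imagio imaging itself is also marked at the biopsy visit. Note 1 says that the baseline and "Biopsy Visits may take place on the same date as the discretion of the investigator".

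On masking, section 4.6 states "No blinding/masking will be conducted", and section 8.2 says "The site investigators will have access to the background clinical information and to the subsequent histopathology report".

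On analysis, section 7.1.3 plans descriptive summaries of feature scores, POM, SenoGram LOM and BI-RADS. For the last of these, "Investigator BI-RADS for breast using SenoGram will be summarized by presenting the frequency and percentage of breast masses in each BI-RADS category". It has no sentence on a mass with two reads.

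**The concern.** The first listed endpoint sets the Imagio assessment beside pathology. The planned order protects that comparison, since scoring is marked at Day 0 and pathology arrives in later columns. A repeat scan is the one permitted event that can fall outside this order. If baseline and biopsy share a date, a scan repeated at a return visit comes after biopsy, and the person scoring it may see the pathology report.

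With no rule in 7.1.3, the analyst appears to have two unattractive choices: a Day 0 score from images judged technically faulty, or a later score that may have been made with knowledge of the biopsy. Section 16 seems to add a third outcome. If late scoring were called a deviation, it would be graded by its effect on a primary endpoint that the document does not designate, and the subject could be removed from an intention-to-diagnose population that 7.3 does not define. In subgroups of 4 to 8, one mass handled differently would show in the tables.

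**Working it through.** The plan gives no figure for repeat scans, so there is nothing of its own to reproduce. The check sets the passages side by side and then looks at scale.

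**Which scan would be used**

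1. Section 4.4 ties the repeat to technical faults in the saved images. The trigger is image quality, not the score.
2. Section 6 gives the core lab charge of every imaging result, including checks of completeness and quality. That covers repeat images, so the upload gap is only an absent mark in Table 1.
3. Section 3.3 treats a subject whose device scans fail the core lab radiologist's review as an enrollment failure, to be replaced.
4. Section 7.3.1 admits to the FAS only subjects with a successful Imagio procedure, and 7.3.2 builds the PP set from the FAS.

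Together, a faulty scan that is not rescued leads to replacement, and a faulty scan that is rescued enters through its repeat. This is an inference, because the word successful is not defined.

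**How late a repeat can be**

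1. Section 4.4 sets no limit of its own.
2. Table 1 allows up to 45 days for biopsy and 60 days for surgery. Note 3 ends the study at definitive diagnosis of the mass.
3. Where biopsy settles the diagnosis, a repeat after the result would fall after the end of study. A repeat read with the result known is therefore confined mainly to subjects awaiting surgical confirmation.
4. Pathology is planned for categories 4a to 5, that is 8 + 4 + 4 + 6 = 22 subjects, and for BI-RADS 3 only as applicable.

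**Whether section 16 excludes anyone**

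That section concerns departures from what the protocol specifies. A repeat scan is expressly permitted in the synopsis and in 4.4, and nothing classes it as a deviation, still less a major one.

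**Scale**

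The quotas in 7.2 are 4 + 4 + 8 + 8 + 4 + 4 + 6 = 38, of which 8 + 8 + 4 + 4 + 6 = 30 are BI-RADS 3 to 5. Assume filled quotas, one mass per subject and subgroups by enrolment category. One mass changing category then moves a percentage by 100/n. If the two POM reads of one mass differ by 10 to 50 points (an assumed range), the group mean moves by that difference divided by n.

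| Group | n | 100/n (points) | Shift in mean POM (points) |
|---|---|---|---|
| 4b or 4c | 4 | 25.0 | 2.5 to 12.5 |
| 5 | 6 | 16.7 | 1.7 to 8.3 |
| 3 or 4a | 8 | 12.5 | 1.25 to 6.25 |
| 3 to 5 together | 30 | 3.3 | 0.33 to 1.67 |

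All 38 is not a suitable denominator. The BI-RADS 1 examples in 7.2 include normal tissue and breast pain, which are not masses, and note 2 to Table 1 makes the duplex scan only possible for BI-RADS 1 and 2.

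The table gives the weight of any single altered value in groups of this size. It does not estimate a bias, since the number of repeats is unknown.

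**The case for a change.** The strongest case for a change is that the text really is silent and a sentence would cost almost nothing. Successful, in 7.3.1, selects subjects and not scores. Section 3.3 does not say whether a rescan is tried before a subject is replaced. Section 6 has the core lab radiologist match the scanned mass against the image-guided biopsy, so an image problem could come to light after biopsy. Section 4.6 relies on prospectively defined procedures and analyses to limit bias, and for a repeat scan that definition is not written down.

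All of this stands as a description of the text. A post-biopsy read by an unmasked investigator remains possible for some subjects, and the replacement reading is the natural one without being stated. What does not follow is a material effect. Unmasked reading is a declared choice throughout the study, so the repeat adds little to a limitation that any report must already acknowledge. Section 4.4 also refers to a separate Scan Protocol, which is not among the documents and may cover repeats.

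The reference in section 16 to an intention-to-diagnose population, and to an undesignated primary endpoint, is a genuine inconsistency. It exists whether or not anyone is rescanned, and the population label looks like a leftover. It has no practical effect here, because 7.3.2 already removes major violations from the PP set.

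**Conclusion.** No change to the plan is called for. The missing sentence on repeat scans is a detail that analysts would fill in the obvious way: summarise the read from the usable scan, and mention in the report any read made after biopsy. The Day 0 order of scoring is sound for every subject scanned once.

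The size cannot be quantified, because no repeat frequency is given. It is bounded in kind: the endpoint summaries are descriptive, sections 7.1.1 and 7.2 plan no hypothesis test, 7.1.3 sets out no sensitivity or specificity estimate, and section 4.1 keeps the device out of clinical decisions. Fixing the Day 0 score in advance would have its own cost, since it could leave a rescanned mass out of subgroups of 4 to 8.

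This rests on two assumptions: that a rescan is prompted by image quality, as 4.4 says, and that the repeat is the scan taken as successful under 7.3.1. If repeats proved common and were mostly read after pathology was known, the comparison with pathology would need a plain caveat in the report.

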4.5. Post-imaging subject evaluation

Immediately after the scan procedure, the subjects will be questioned to assess for:

- Any adverse device event/effect

4.6. Minimization of Bias

Potential for bias during this clinical investigation has been minimized by a well-controlled design, expected conduct under the terms of an approved study protocol, use of specific inclusion and exclusion criteria, careful definitions for study procedures and outcomes and prospectively defined methods of data analysis. No blinding/masking will be conducted.

5. SCHEDULE OF EVENTS

Table 1 shows the schedule of events for this study

Table 1. Schedule of events

Evaluation	Screening/ Enrollment/Baseline Imaging Visit ¹ Day 0	Breast and Lymph Node Biopsy Visit (if not done on same day as baseline) May be repeated if issue with initial biopsy *Up to 45 days from baseline	Breast and Lymph Node (as applicable) Surgery *Up to 60 Days from baseline
Informed Consent	X		
Breast/Lymph Node Medical History	X		
I/E Criteria	X		
CDU (including elastography and doppler as applicable) and SOC Imaging	X		
Imagio Imaging (including Elastography and Doppler as applicable) of breast and lymph node (as applicable). This includes biopsy imaging as applicable	X ²	X	
SOC + Imagio Imaging uploaded to Core Lab	X		
SOC Imaging, Imagio IUS and/or IUS+OA POM and BI-RADS Scoring	X		
Pathology/Surgical Reports as applicable		X	X
Adverse Event/Effect	X		
End of Study	X ³	X ³	X ³

¹The Screening/Enrollment/ Imaging, and Biopsy Visits may take place on the same date as the discretion of the investigator

² BI-RADS 1 and 2 abnormalities will be scanned with the ultrasound only probe and possibly the duplex OA/US probe. BI-RADS 3-5 masses will be scanned with both probes.

³ Study will end at the final definitive diagnosis of the breast mass which could include confirmation via surgery report

6. IMAGING DATA EVALUATIONS

All imaging results will be managed by an independent Imaging Core Lab, who will perform QA review of de-identified collected images and assembly of the designated image sets. A QA evaluator who is a QAR will perform an image/lesion pairing assessment once the core lab performs the QA of all demographic data, checks image completeness and quality, and resolves all discrepancies.

The QARs will check if lesions/masses scanned with Imagio at the site match the same lesion(s)/mass(es) seen on all imaging modalities at the site as well as on the image guided biopsy.

The Imaging Core Lab to be used in the study is:

American College of Radiology (ACR)
 Center for Research and Innovation
 [name]
 [name]
 [name]
 United States of America

7. STATISTICAL CONSIDERATIONS

7.1. Statistical design and methods

7.1.1. General Statistical Considerations

Summaries of each study endpoint and other clinical/demographic/safety data will be provided overall and by BI-RADS of the breast masses to evaluate the consistency of the results across different type of breast masses with respect to BI-RADS. Additional analyses by clinical and/or demographic subgroups may be performed. Confidence intervals will be calculated at a 95% confidence level, unless otherwise specified. Given the nature of the study, no formal statistical hypothesis testing is planned for this study.

7.1.2. Demographics, Medical History, and Other Baseline Characteristics

For the full analysis set (FAS) population (defined in section 6.3), baseline subject characteristics will be tabulated. Baseline subject characteristics will comprise the following: subject demographics (gender, age, race, ethnicity), height, weight, Fitzpatrick skin type, menopausal status, cup size, Standard of Care (SOC) imaging (i.e. mammography, CDU, and magnetic resonance imaging) POM and BI-RADS, breast mass location and depth and size, lymph node location and size and depth, breast and lymph node medical/surgical history.

For baseline subject characteristics that are continuous variables, the following descriptive statistics will be given: number of observations, mean, standard deviation, minimum, maximum, and median. For subject characteristics that are categorical variables, the frequency and percentage of subjects in each category will be provided. Summary tables will display demographic and baseline characteristics overall and by BI-RADS of the breast masses (3, 4a, 4b, 4c, 5).

7.1.3. Analysis of Study Endpoints

Breast mass site pathology diagnosis (benign, malignant, high risk) will be summarized by presenting the frequency and percentage of breast masses in each BI-RADS category. A listing of the pathology results (benign specification, malignant specification, high risk specification) will be presented.

Breast mass feature scores

Each of the following breast mass feature score data will be summarized by presenting the mean, standard deviation, number of observations, median, quartiles, minimum, and maximum:

- For IUS:
 - External peripheral zone score (range 0-5)
 - External capsular/boundary zone score (range 0-6)
 - Internal shape score (range 0-5)
 - Internal sound transmission score (range 0-5)
 - Internal echotexture score (range 0-5)
- For OA/US:
 - External peripheral zone radiating vessel score (range 0-5)
 - External capsular/boundary zone vessel score (range 0-6)
 - Internal vessel score (range 0-5)
 - Internal deoxygenated blush score (range 0-5)
 - Internal total hemoglobin score (range 0-5)

3. Imago/OA/US POM and BI-RADS for breast using SenoGram

Investigator POM for breast using SenoGram will be summarized by presenting the mean, standard deviation, number of observations, median, quartiles, minimum, and maximum. Investigator BI-RADS for breast using SenoGram will be summarized by presenting the frequency and percentage of breast masses in each BI-RADS category. SenoGram LOM for breast will also be summarized by presenting the mean, standard deviation, number of observations, median, quartiles, minimum, and maximum.

Lymph node scoring

Lymph node scoring (shape score, cortical thickness score, margin score, hilar compression-displacement score, and size) will be summarized by presenting the frequency and percentage of lymph nodes in each category. The total score will be summarized by presenting the mean, standard deviation, number of observations, median, quartiles, minimum, and maximum. Imago IUS classification of lymph node will be summarized by presenting the frequency and percentage of lymph nodes in each category.

Lymph node site pathology (histopathology and cytopathology) results will be summarized by presenting the frequency and percentage of lymph nodes in each histopathology (positive for malignancy, negative for malignancy, indeterminate, extracapsular extension) and cytopathology (positive malignancy, negative for malignancy, indeterminate, other) category. A listing of pathology results will also be presented.

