Indication for Use	
The Imagio Breast Imaging System is indicated for use by a trained and qualified healthcare provider for evaluation of palpable and non-palpable breast abnormalities in adult subjects who are referred for a diagnostic imaging breast work-up, following clinical presentation or either screening or diagnostic mammography or other imaging examinations. The ultrasound mode should be initially used in a targeted fashion, to assess any focal area(s) of clinical or imaging concerns. In ultrasound (US) mode, the device can be used to assign a BI-RADS (Breast Imaging-Reporting and Data System) category to either breast tissue or a mass that is causing clinical or imaging concerns. Masses that are classified as BI-RADS categories 3 through 5 can then be assessed using the Opto-Acoustic (OA) mode. In the OA mode, the Imagio Breast Imaging System provides information about the central nidus, boundary and peripheral zones, based on vascularity and blood oxygen saturation of the imaged tissues, to assist in the diagnosis of the benign or malignant mass(es) of interest. For ultrasound BI-RADS 3-5 masses, using the OA features of the mass allows for improved classification of the mass of interest as compared to ultrasound alone. The OA mode is not indicated for ultrasound BI-RADS 1 and 2 findings. The Imagio Breast Imaging System includes an artificial intelligence (AI) based software function to assist the users in assessing the BI-RADS Classifications. This device is not intended to be used as a replacement for mammographic screening or for definitive pathologic diagnosis.

Sponsor	
Name	
Seno Medical Instruments, Inc. [name] United States of America

Contact details	
[name] Vice President of Clinical Operations [contact]

Investigation centers	
Number of centers	One (1)
Location of centers	USA
Clinical investigation design	
Objectives	
 1. Obtain ultrasound only probe images and duplex probe OA/US (both gray scale and OA) probe images. This includes doppler and elastography imaging with the gray scale only ultrasound probe and ultrasound mode of the duplex OA/US probe. 2. Provide breast and lymph node pathology results (except BI-RADS 1, 2 and 3 (as applicable))
Endpoints	
 - Imagio (IUS+OA) vs Pathology Result assessment - Adverse Event Assessment

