2. STUDY DESIGN AND OBJECTIVES

This clinical investigation is designed to evaluate the images produced by the Gen 2 Imagio System in a clinical setting.

The primary objectives of this study are:

1. Obtain ultrasound only probe images and OA/US (both gray scale and OA) probe images. This includes doppler and elastography imaging with gray scale only ultrasound probe and ultrasound mode of the duplex OA/US probe.
2. Provide breast and lymph node pathology results (except BI-RADS 1, 2 and 3 (as applicable))

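### Section 7.1.3 tabulates Imagio IUS node classification and node pathology separately, so the planned analyses cannot show how the two relate

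*Combined protocol and SAP*

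**What the plan says.** The Synopsis lists two endpoints: adverse events and "Imagio (IUS+OA) vs Pathology Result assessment". Objective 2 in Section 2 is to "Provide breast and lymph node pathology results (except BI-RADS 1, 2 and 3 (as applicable"; it does not mention agreement with imaging.

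Section 7.1.3, Analysis of Study Endpoints, plans the following for nodes:

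- **Score components:** the list ends "hilar compression-displacement score, and size) will be summarized by presenting the frequency and percentage of lymph nodes in each category". The total score gets summary statistics.
- **Imagio classification:** "IUS classification of lymph node will be summarized by presenting the frequency and percentage of lymph nodes in each category". The categories are not named.
- **Histopathology:** a frequency table with the categories "positive for malignancy, negative for malignancy, indeterminate, extracapsular extension".
- **Cytopathology:** a separate frequency table with the categories "positive malignancy, negative for malignancy, indeterminate, other".
- **Listing:** "A listing of pathology results will also be presented". It is not said to carry the Imagio classification.

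Section 7.1.1 says that summaries are "provided overall and by BI-RADS of the breast masses to evaluate the consistency of the results". Section 7.3.2 repeats this stratification for the per-protocol population.

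**The concern.** Node scoring, node classification and node pathology all sit under the heading for endpoint analyses. They are not safety data, so the only listed endpoint they can serve is the comparison of Imagio with pathology. Nodes are not incidental either: they are imaged where applicable (Section 4.4), scored, and followed to pathology (Section 4.3), and Section 7.2 justifies the sample size partly by the cross section of nodes it will supply.

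Yet no planned table, paired listing or agreement measure links a node's Imagio result to its own pathology. Stratifying by the BI-RADS category of the breast mass does not create that link. A cross-tabulation made after the data are in would have to be labelled unplanned under Section 7.6.

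A smaller question concerns coding. Extracapsular extension describes a node that already contains tumour, yet it stands beside the positive category with no rule for counting a node that has both.

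**Working it through.** **The plan's own figure.** The BI-RADS strata in Section 7.2 add up: 4 + 4 + 8 + 8 + 4 + 4 + 6 = 38. BI-RADS 4 and 5 supply 8 + 4 + 4 + 6 = 22 subjects; adding the 8 with BI-RADS 3 gives 30. No number of nodes is stated, so every node count below is an assumption. The value 22 corresponds to one node per planned BI-RADS 4 or 5 subject.

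**What separate tables allow.** Let n be the nodes with both results, a the number classed suspicious by Imagio (an assumed two-level reading of the unnamed categories), and b the number positive on pathology. The tables give a and b but not TP, the number that are both.

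- Bounds: max(0, a + b − n) ≤ TP ≤ min(a, b)
- Agreement = (n − a − b + 2TP)/n
- Sensitivity = TP/b

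| n | a | b | TP range | Agreement | Sensitivity |
|---|---|---|---|---|---|
| 22 | 8 | 8 | 0 to 8 | 6/22 = 27% to 22/22 = 100% | 0% to 100% |
| 22 | 8 | 6 | 0 to 6 | 8/22 = 36% to 20/22 = 91% | 0% to 100% |
| 22 | 3 | 3 | 0 to 3 | 16/22 = 73% to 22/22 = 100% | 0% to 100% |
| 10 | 4 | 4 | 0 to 4 | 2/10 = 20% to 10/10 = 100% | 0% to 100% |

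In the first row, chance agreement is (8×8 + 14×14)/22² = 260/484 = 0.537. Kappa at the lower end is therefore (0.273 − 0.537)/(1 − 0.537) = −0.57; at the upper end it is 1.

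These bounds assume that both tables cover the same nodes. They may not: Section 4.3 lists pathology only for BI-RADS 3 (as applicable), 4 and 5, and Section 7.4 analyses available cases without imputation.

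**Extracapsular extension.** Assume 22 nodes, 8 positive, 4 of them with extension. If the rows are exclusive, the positive row shows (8 − 4)/22 = 18% instead of 8/22 = 36%. If more than one row may be ticked, the rows total (22 + 4)/22 = 118%.

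**Precision once the tables are joined.** Exact (Clopper-Pearson) 95% intervals for observed agreement near 80%, treating nodes as independent:

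- 8/10: 0.44 to 0.97
- 18/22: 0.60 to 0.95
- 24/30: 0.61 to 0.92

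**The case against.** The strongest reply is that the plan never promised node agreement. The endpoint names IUS+OA, while the only node classification is IUS alone and no OA node score is planned. The POM and BI-RADS results after SenoGram are for the breast mass. Objective 2 asks only that pathology be provided, which the planned frequencies and listing do. The study is a first clinical look at Gen 2 images, with no hypothesis test and no power calculation. All of this stands. It means that the plan leaves the role of the node data undefined, and that a node comparison can be descriptive only. It does not explain why node data sit among the endpoint analyses without any link to pathology.

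A second reply is that joining the tables is not free. Section 6 describes matching lesions and masses across imaging and biopsy but does not name nodes, so nothing states that the scored node is the one sampled or excised. Some scored nodes may have no pathology. This also stands, and the fix has to allow for it.

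A third reply is that nothing says the histopathology categories are exclusive. That is right. A reader might infer that positives will be undercounted, but the text supports only that they would be if the rows were coded as exclusive. Taken alone, this is a coding clarification.

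**Conclusion.** The point holds for the planned analyses. As written, they cannot show how Imagio IUS node classification relates to node pathology. In the assumed 22-node example with 8 and 8, agreement could be anything from 27% to 100%. All such figures rest on assumed node counts and on a two-level classification.

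Three stronger readings are tempting but unsupported:

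- **That the study itself cannot answer the question.** Node scores and node pathology are both on the data list in Section 4.3, and Section 7.6 permits unplanned analyses if they are labelled.
- **That separate tables carry no information on agreement.** They bound it, sometimes usefully, as in the 73% to 100% case, although sensitivity there still runs from 0% to 100%.
- **That a stated objective is left unmet.** Node agreement is not named as one.

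This is a worthwhile, low-cost improvement to a descriptive study. It does not threaten the study's validity.

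**What to change.** 1. State in Section 7.1.3 that the node comparison is a descriptive, IUS-only part of the Imagio-versus-pathology endpoint.
2. Pre-specify a per-node cross-tabulation of Imagio IUS classification by one final node pathology result: positive, negative, or indeterminate/other. Name the classification categories, and give a rule for nodes that have both cytology and histology.
3. Summarize the total node score by the same pathology result.
4. Restrict both to nodes where the scored node is matched to the sampled node. Report the numbers of nodes, of subjects, and of scored nodes without pathology.
5. Give exact 95% CIs, and state how they are to be read if a subject contributes more than one node.
6. Show extracapsular extension as a sub-row of the positive category.

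The cost is one extra table, a changed row and a node-matching check. The documents list no further visit or procedure that this would need, but they do not show that the matching is already recorded. The estimates will be imprecise and will apply only to nodes with pathology.
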